## Appendix F Immunotherapy efficacy assessment instruments

### Mini-RQLQ

Please complete all questions by circling the number that best describes how troubled you have been during the last week as a result of your nose/eye symptoms.

	Not troubled	Hardly troubled at all	Somewhat troubled	Moderately troubled	Quite a bit troubled	Very troubled	Extremely troubled
Activities							
1. Regular activities at home and at work (your occupation or tasks that you have to do regularly around your home and/or garden)	0	1	2	3	4	5	6
2. Recreational activities (indoor and outdoor activities with friends and family, sports, social activities, hobbies)	0	1	2	3	4	5	6
3. Sleep (difficulties getting a good night's sleep and/or getting to sleep at night)	0	1	2	3	4	5	6
Practical problems							
4. Need to rub nose/eyes	0	1	2	3	4	5	6
5. Need to blow nose repeatedly	0	1	2	3	4	5	6
Nose symptoms							
6. Sneezing	0	1	2	3	4	5	6
7. Stuffy blocked nose	0	1	2	3	4	5	6
8. Runny nose	0	1	2	3	4	5	6
Eye symptoms							
9. Itchy eyes	0	1	2	3	4	5	6
10. Sore eyes	0	1	2	3	4	5	6
11. Watery eyes	0	1	2	3	4	5	6
Other symptoms							
12. Tiredness and/or fatigue	0	1	2	3	4	5	6
13. Thirst	0	1	2	3	4	5	6
14. Feeling irritable	0	1	2	3	4	5	6

### Total Nasal Symptoms Score (TNSS)

The Total Nasal Symptom Score (TNSS; possible score of 0-12) is the sum of 4 individual participant-assessed symptom scores for rhinorrhea, nasal congestion, nasal itching, and sneezing, each evaluated using a scale of 0=None, 1=Mild, 2=Moderate, or 3=Severe.

---

## **Appendix G Allergens used for skin prick testing**

Type	Allergen	Stock Concentration	Manufacturer
Tree	Oak	20,000 PNU/ml	Greer
Tree	Birch	20,000 BAU/ml	Greer
Tree	Beech	20,000 BAU/ml	Greer
Tree	Elm	20,000 BAU/ml	Greer
Tree	Ash	20,000 BAU/ml	Greer
Tree	Sycamore	20,000 BAU/ml	Greer
Tree	Poplar	20,000 BAU/ml	Greer
Tree	Hickory	20,000 BAU/ml	Greer
Tree	Walnut	20,000 BAU/ml	Greer
Tree	Mulberry	20,000 BAU/ml	Greer
Tree	Pine	20,000 BAU/ml	Greer
Tree	Willow	20,000 BAU/ml	Greer
Grass	Timothy	100,000 BAU/ml	Greer
Grass	Orchard	100,000 BAU/ml	Greer
Grass	Johnson	100,000 BAU/ml	Greer
Grass	June	100,000 BAU/ml	Greer
Grass	Rye	100,000 BAU/ml	Greer
Grass	Fescue	100,000 BAU/ml	Greer
Grass	Bermuda	10,000 BAU/ml	Greer
Weed	Ragweed	100,000 AU/ml	Greer
Weed	Plantain	40,000 PNU/ml	Greer
Weed	Pigweed	40,000 PNU/ml	Greer
Weed	Lambsquarter	40,000 PNU/ml	Greer
Weed	Sage/Mugwart	40,000 PNU/ml	Greer
Weed	Sheep Sorrel	40,000 PNU/ml	Greer
Weed	Cocklebur	40,000 PNU/ml	Greer
Mold	Aspergillus	40,000 PNU/ml	Greer
Mold	Penicillium	40,000 PNU/ml	Greer
Mold	Mucor	40,000 PNU/ml	Greer
Mold	Fusarium	40,000 PNU/ml	Greer
Mold	Alternaria	40,000 PNU/ml	Greer
Mold	Helminthosporium	40,000 PNU/ml	Greer
Mold	Botrytis	40,000 PNU/ml	Greer
Mold	Cladosporium	40,000 PNU/ml	Greer
Mold	Curvularia	40,000 PNU/ml	Greer
Animal	Cat Hair	10,000 BAU/ml	Greer

---

Animal	AP Cat	10,000 BAU/ml	Hollister
Animal	Dog epithelia	20,000 PNU/ml	Greer
Animal	AP Dog	10,000 PNU/ml	Hollister
Animal	Mouse	20,000 PNU/ml	Greer
Animal	Cockroach Mix	20,000 PNU/ml	Greer
Animal	Rat	20,000 PNU/ml	Greer
Animal	Horse	20,000 PNU/ml	Greer
Animal	Rabbit	20,000 PNU/ml	Greer
Dust Mite	D. farinae	10,000 BAU/ml	Greer
Dust Mite	D. pteronyssinus	10,000 BAU/ml	Greer
Control	Saline		Hollister
Control	Histamine	1mg/ml	Hollister

---

## **Appendix H Immunotherapy Injection Schedule**

Visit Day	Vial Number	Dilution	A, B, C (ml)	Injection Volume (ml)
2	#5	1:625	0.05	0.15
3	#5	1:625	0.10	0.30
4	#5	1:625	0.15	0.45
5	#5	1:625	0.20	0.60
6	#4	1:125	0.05	0.15
7	#4	1:125	0.10	0.30
8	#4	1:125	0.15	0.45
9	#4	1:125	0.20	0.60
10	#3	1:25	0.05	0.15
11	#3	1:25	0.10	0.30
12	#3	1:25	0.15	0.45
13	#3	1:25	0.20	0.60
14	#2	1:5	0.05	0.15
15	#2	1:5	0.10	0.30
16	#2	1:5	0.15	0.45
17	#2	1:5	0.20	0.60

---

## Appendix I Allergy Rescue Medication Action Plan

Ask patient if symptoms are adequately controlled at each bi-weekly visit. The response dictates whether a medication is added or subtracted. Resuce medications will not be increased after week 10.

Symptoms Controlled?	Medication Action
no	Add medication
yes	Subtract medication

Step	Rescue Medication	Score
A	None	0 points
B	Loratadine 10mg PO Daily	1 point
C	Loratadine 10mg PO BID	2 points
D	Loratadine BID plus Triamcinolone Daily	4 points
E	Loratadine BID plus Triamcinolone BID	6 points
F	Loratadine BID plus Triamcinolone BID plus Prednisone 5mg Daily	9 points
G	Loratadine BID plus Triamcinolone BID plus Prednisone 5mg BID	12 points

**Note:** To calculate the daily medication score add the total points for all medications noted above. Any other allergy rescue medications inadvertently added will also be counted in a similar manner as follows; other oral antihistamines (1 points each tablet), ophthalmic allergy medications (1 points each use), other nasal steroids, cromolyn, azelastine (2 points daily, 4 points BID). Symptoms and medication use are recorded daily at home.

---

Appendix J Clinical Visit Summary

Subject ID	Date	Visit #
-------------------	-------------	----------------

**Initials**

Allergy medications currently taking \_\_\_\_\_  
\_\_\_\_\_

Daily symptom cards collected Y/N

Today's RQLQ \_\_\_\_\_

Baseline RQLQ \_\_\_\_\_

Symptoms controlled Y/N

Medication added \_\_\_\_\_

Medication removed \_\_\_\_\_

Initial Vitals	P	BP	RR	Temp	Sats	PFR	Time	Initials
----------------	---	----	----	------	------	-----	------	----------

Physical Exam	_____						Time	Initials
---------------	-------	--	--	--	--	--	------	----------

Vial ID	_____	Vial #	_____	Dose (ml)	_____	Time	Initials
---------	-------	--------	-------	-----------	-------	------	----------

Exit Vitals	P	BP		Sats	PFR	Time	Initials
-------------	---	----	--	------	-----	------	----------

Reactions or Other Notes \_\_\_\_\_  
\_\_\_\_\_

**Appendix K Symptom and Medication Card**

**Daily Symptoms and Medication Use**

Initials

ID

Date				
Symptoms	None	Mild	Mod	Severe
Runny nose	0	1	2	3
Nasal stuffiness	0	1	2	3
Nasal itching	0	1	2	3
Sneezing	0	1	2	3
Medications Taken				
Loratadine tablet				
Triamcinolone spray				
Prednisone tablet				
Other medications	<hr/>			

Date				
Symptoms	None	Mild	Mod	Severe
Runny nose	0	1	2	3
Nasal stuffiness	0	1	2	3
Nasal itching	0	1	2	3
Sneezing	0	1	2	3
Medications Taken				
Loratadine tablet				
Triamcinolone spray				
Prednisone tablet				
Other medications	<hr/>			

Date				
Symptoms	None	Mild	Mod	Severe
Runny nose	0	1	2	3
Nasal stuffiness	0	1	2	3
Nasal itching	0	1	2	3
Sneezing	0	1	2	3
Medications Taken				
Loratadine tablet				
Triamcinolone spray				
Prednisone tablet				
Other medications	<hr/>			

Date				
Symptoms	None	Mild	Mod	Severe
Runny nose	0	1	2	3
Nasal stuffiness	0	1	2	3
Nasal itching	0	1	2	3
Sneezing	0	1	2	3
Medications Taken				
Loratadine tablet				
Triamcinolone spray				
Prednisone tablet				
Other medications	<hr/>			

*Try to fill out this card every day at the same time before you go to bed.*

*If found please return to [name] [name]*

The purpose of this document is to provide a description of the statistical methods and procedures to be implemented for the analysis of data derived from the study entitled: “A double-blind, prospective, parallel group evaluation of a novel biologic therapy for perennial allergic rhinitis” sponsored by Relez Therapeutics, LLC, and conducted at the Johns Hopkins Bayview Medical Center, Baltimore, Maryland. The protocol version used for the plan is Version 6.9 dated February 10, 2017. At the time of development of this statistical analysis plan (SAP) the study Principal Investigator is [name], Johns Hopkins University School of Medicine, Baltimore, MD

Any revisions to the SAP (both alternative and additional methods) will be made prior to database lock and reasons for such revisions will be described in the final Clinical Study Report (CSR).

## **STUDY OVERVIEW**

### **Endpoints**

#### **Primary Endpoints**

The primary endpoint is to quantify and compare the clinical difference in signs and symptoms and medication usage as well as the global RQLQ index that may be apparent when subjects with active perennial allergic rhinitis (PAR) with or without seasonal symptoms (SAR) are treated in a double-blind, prospective, controlled eight weeks study with a proprietary mixture of FDA approved allergens (PMA) versus placebo.

#### **Secondary Endpoint**

The secondary endpoints include a symptom score trend analysis, drop out rates, and adverse events profile (AE). Serum will also be stored for measurement of immunoglobulins at a later time.

## STUDY DESIGN AND METHODS

### Study Design

This is a phase 2 proof of concept study. It is being undertaken to characterize and quantify the clinical difference in signs and symptoms that may evolve when subjects with active seasonal or perennial allergic rhinitis (SAR/PAR) are administered a sub-cutaneous form of immunotherapy in a double-blind, prospective, controlled six weeks study wherein a proprietary mixture of FDA approved allergens (PMA) is compared with saline placebo.

Randomization to active PMA versus placebo treatment is on a 1 to 1 ratio. A double-blind study design is used to minimize outcome bias. Randomization measures to minimize bias at study entry include computerized random assignment of treatment versus placebo vials.

Subjects who are receiving nasal steroids for their SAR/PAR at screening may continue in the screening process if they agree to discontinue their therapy and commence a 14-day wash-out period of their medication prior to receiving active/placebo immunotherapy. Potential study subjects who, at screening, are not on active treatment for their SAR/PAR and asthma may enter directly into the investigation provided they fulfil entry and exclusion criteria and screening testing requirements.

The population to be studied consists of male and female adults aged 18 years to 65 years who are actively manifesting SAR/PAR have a score of at least 28 on the mini-RQLQ and 6 on the TNSS scale.

[figure not shown]
The active treatment phase of the study will be for six weeks with a safety follow-up assessment at 30 days post-treatment. No interim analysis is planned.

The study immunotherapy that will be evaluated in this study is a new innovative proprietary mixture of FDA approved allergens which has been clinically developed and evaluated, during the past three decades, in some 20,000 patients by the inventor of the mixture (see 3.2). In clinical evaluation this patented antigen mixture has provided clinical symptomatic relief to patients with SAR/PAR in as brief a period as three administrations of immunotherapy injections and has an observed overall success rate of approximately 80 to 90 percent of such treated subjects.

In this study approximately 36 study subjects will be equally randomized to active PMA or placebo. The duration of active PMA or placebo treatment will be 8 weeks with clinic visits twice-weekly during this period and a post-treatment safety follow up assessment at one month following the final administration of immunotherapy. All doses of immunotherapy will be administered in the study site clinic by the investigators or their designees.

A schematic of the study design is included in the Figure below. A schedule of assessments is listed in **Error! Reference source not found.** of the protocol.

Figure Schematic of Study Design

The SAP will follow the study protocol sections 12.1 to 12.3. Statistical methodology was developed in conjunction with the faculty of the Johns Hopkins Bloomberg School of Public Health Department of Biostatistics. Specific calculations include the following wherein "p" values as well as 95% confidence intervals will be calculated.

### Primary Outcomes

1. Daily Combined Score (DCS) – Comparison of the delta visit 2 to visit 17 (change in score) between both treatment groups I and II using an unpaired t test.
2. Daily Combined Score (DCS) – Comparison of the delta visit 2 to visit 18 (change in score) between both treatment groups I and II using an unpaired t test.
3. mini-rhinoconjunctivitis quality of life questionnaire (RQLQ) - Comparison of the delta visit 2 to visit 17 (change in score) between both treatment groups I and II using an unpaired t test.
4. mini-RQLQ - Comparison of the delta visit 2 to visit 18 (change in score) between both treatment groups I and II using an unpaired t test.

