### **Sample Size Justification:**

The study sample size is based upon the results of prior immunotherapy investigations undertaken by the Investigators of this study and their colleagues in the Division of Allergy & Clinical Immunology, Johns Hopkins University School of Medicine. Efficacy for immunotherapy was estimated to be 80% for treatment group and 30% for placebo. Using an error rate ( $\alpha$ ) of 0.05 and 80% Power we calculate a total sample size needed of 28 subjects. To account for drop off we will recruit up to 36 subjects.

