#### **12.1.1 Analysis Sets**

All efficacy and safety analyses will be analyzed using the full analysis set (FAS). The FAS will consist of all subjects who were randomized and received at least one dose of double-blind study immunotherapy. Efficacy analyses will be analyzed according to the treatment received and safety analyses will be analyzed according to the actual treatment received.

Unless otherwise specified, all statistical tests and confidence intervals will be two-sided and conducted at the 0.05 significance level.

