#### **12.1.3 Efficacy Analysis**

The intent-to-treat approach will be used. Baseline characteristics will be described using mean and standard deviation for continuous variables and medians and ranges for discrete variables. The primary efficacy variable of comparing PMA versus placebo will be undertaken by quantifying the instrument-assessment scores of each study subject in each of the two therapeutic arms of the investigation. The p-value, least square (LS) treatment means, difference between the LS treatment means, and 95% confidence intervals for the treatment differences will be presented. The success of blinding will be assessed by asking the patient and staff which treatment set they thought they were getting, i.e. active treatment or placebo. The results will be recorded at each study visit.

Total Nasal Symptoms Score (TNSS) and the Mini-RQLQ attached in Appendix F will be used to evaluate clinical efficacy. TNSS along with rescue medication use is recorded at home on a daily

card as shown in Appendix K. Daily scores will only be recorded on weeks 2, 10, and 14. The mini-RQLQ will be recorded in person at screening, during each study visit, and at followup. The correct use of the TNSS survey is to score 0-12 based on symptoms reported that day while the mini-RQLQ is scored 0-84 based on symptoms reported over the past week. Higher scores indicate worse symptoms.

The primary outcome measure is the average daily combined score (DCS) which is calculated by adding the average TNSS + average medication score as well as the mini-RQLQ at weeks 2,10 and 14.

Secondary outcomes will include the adverse events rate and TNSS between both groups using a one-tailed Fischer's exact test and/or unpaired t test.

Other outcomes include baseline characteristics, use of epinephrine, and drop out between both treatment groups I and II using a one-tailed Fischer's exact test and/or unpaired t test. Trend tests for comparison of both groups will be performed such as the Jonckheere-Terptsra trend test. A sum of Mann-Whitney-Wilcoxon tests may also be sensitive and reveal a mild trend. Other trend tests may also be used.

A Kaplan-Meier or similar product limit estimator function will also be used to calculate the effect of treatment over time.

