#### **12.3 Determination of Sample Size**

The study sample size is based upon the results of prior immunotherapy investigations undertaken by the Investigators of this study and their colleagues in the Division of Allergy & Clinical Immunology, Johns Hopkins University School of Medicine. Efficacy for immunotherapy was estimated to be 80% for treatment group and 30% for placebo. Using an error rate ( $\alpha$ ) of 0.05 and 80% Power we calculate a total sample size needed of 28 subjects. To account for drop off we will recruit up to 36 subjects.

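### The SAP has no rule for a missing visit 17 or 18 score, so the four primary t tests default to observed cases although the protocol declares intent-to-treat

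*Combined protocol and SAP*

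**What the plan says.** **Primary test.** SAP, Primary Outcomes, lists DCS and mini-RQLQ, each from visit 2 to visit 17 and from visit 2 to visit 18. All four use the same form: "Comparison of the delta visit 2 to visit 17 (change in score) between both treatment groups I and II using an unpaired t test".

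**Population.** Protocol 12.1.3 states: "The intent-to-treat approach will be used". Protocol 12.1.1 adds: "The FAS will consist of all subjects who were randomized and received at least one dose of double-blind study immunotherapy". Completing treatment is not required. The SAP, under Study Design, takes this over: "The SAP will follow the study protocol sections 12.1 to 12.3".

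**Grouping.** Protocol 12.1.1 also says: "Efficacy analyses will be analyzed according to the treatment received".

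**Estimator.** Protocol 12.1.3 promises "The p-value, least square (LS) treatment means, difference between the LS treatment means", which suggests a fitted model. The SAP names only the t test.

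**Expected loss.** Protocol 12.3 and the study summary arrive at 28 subjects and continue: "To account for drop off we will recruit up to 36 subjects". No drop-out rate is given.

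**Data collected.** Under protocol 12.1.3 the mini-RQLQ is taken at screening, at every study visit and at follow-up. The diary behind the DCS is kept only in weeks 2, 10 and 14. Protocol 8.3.4 includes an efficacy assessment at early termination but does not say which analysis visit it feeds.

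**Handling of missing scores.** Neither protocol section 12 nor the SAP gives an imputation rule, a missing-data model or a sensitivity analysis. The SAP compares drop-out rates between groups and lists a repeated-measures option for mini-RQLQ, both under Other Comparisons and Outcomes and outside the primary analysis.

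**The concern.** A change score needs both values. Once some subjects lack the later one, the specified test cannot be run on the declared population, and the analyst must choose a set that the plan has not named. That set may also differ between visits 17 and 18.

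The loss need not be unrelated to outcome or arm. The study summary plans to tabulate stopping for intolerance or lack of efficacy by group, and protocol 6.4 withdraws subjects from the study after a systemic reaction of Grade 3 or more. If subjects leave for different reasons in the two arms, a comparison of those still observed is no longer protected by randomisation. Mini-RQLQ scores recorded before a subject left, which carry information about the missing value, are not used.

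**Working it through.** **1. The plan's own figure.** Inputs from protocol 12.3: "Efficacy for immunotherapy was estimated to be 80% for treatment group and 30% for placebo", alpha 0.05, power 80%. Two-sided testing is set in 12.1.1.
- Pooled normal formula: n per arm = [1.96 × sqrt(2 × 0.55 × 0.45) + 0.842 × sqrt(0.16 + 0.21)]² / 0.50² = 14.3, so 15 per arm and 30 in total.
- Arcsine formula: 14.1 per arm, about 28 in total.
- Power with 14 per arm: 79.1%.

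The stated 28 is reproduced. The implied allowance is (36 - 28)/36 = 22.2%, and 28/(1 - 0.222) = 36. The 22% is derived from these totals.

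**2. Precision.** sqrt(36/28) = 1.134, so standard errors are 13% larger with 28 subjects than with 36. The sample size already allows for this.

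**3. How observed-case bias arises.** Assume 18 per arm and 8 missing. Let g be the gap, in SD of change, between observed and missing subjects, equal in both arms. The bias in the difference is g × (missing in active - missing in placebo)/18.

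| Missing, active/placebo | g = 0.25 | g = 0.5 | g = 1.0 |
|---|---|---|---|
| 4/4 | 0 | 0 | 0 |
| 2/6 | -0.06 | -0.11 | -0.22 |
| 0/8 | -0.11 | -0.22 | -0.44 |

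Reversing the split or the sign of g reverses the sign of the bias. The documents fix neither.

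**4. Simulation on the mini-RQLQ scale.** All inputs are assumptions: SD 14, correlation 0.8^lag, five visits, no true effect, 21 to 27% drop-out, active subjects leaving at random. The difference is active minus placebo, and a negative value favours active.
- Placebo drop-out driven by the level of the score: about -0.1 to -0.95 points, depending on the strength of the dependence.
- Placebo drop-out driven by worsening from baseline: +0.8 to +2.6 points.
- Both arms dropping out alike: near zero.
- Likelihood-based estimate: within about 0.05 of zero. Drop-out here depended on observed scores, which is the condition that method needs.

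**5. Bias against noise.** SD of change = 14 × sqrt(2 × (1 - 0.8⁴)) = 15.2. The standard error with 14 per arm = 15.2 × sqrt(2/14) = 5.75.
- 0.95/5.75 = 0.17 SE. Two-sided false-positive risk moves from 5.0% to about 5.3%.
- 2.6/5.75 = 0.45 SE. The normal approximation gives P(Z > 1.51) + P(Z < -2.41) = 0.066 + 0.008, about 7.4%. This bias runs against active treatment.

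**6. Gain from baseline adjustment.** With equal variances and baseline-to-final correlation r, the variance of the adjusted difference relative to the change-score difference is (1 - r²)/(2(1 - r)) = (1 + r)/2.
- r = 0.3: 0.65, SE smaller by 1 - sqrt(0.65) = 19%.
- r = 0.7: 0.85, SE smaller by 1 - sqrt(0.85) = 8%.

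The documents give no r, so this range is assumed.

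**The case against.** **A reader might infer that the plan prescribes a completers-only analysis.** It does not. No section restricts the test to completers, and the declared set is everyone randomised and dosed. The default set is subjects observed at the visit, which can include people who missed injections but attended. The defect is a missing rule.

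**A reader might infer a known bias in favour of PMA.** The documents give no SD, correlation or drop-out pattern. The simulated bias changes sign with the mechanism and is well below one standard error in a trial of this size. This objection stands against quoting any single figure. It does not show that the bias is harmless or conservative.

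**Other provisions might be thought to cover the gap.** Protocol 12.1 plans a blinded review of evaluability and methods, 8.3.4 provides an early-termination assessment, and the SAP lists a repeated-measures option and a drop-out comparison. None tells the analyst what to do in the primary test when a score is missing.

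**A t test on change is a simple, legitimate choice for a proof-of-concept trial.** That is fair, but it still needs a missing-data rule, and baseline adjustment is usually more precise at no extra data cost.

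**A mixed model has limits here.** This stands. With DCS diaries only in weeks 2, 10 and 14, a subject lost before week 10 has no post-baseline DCS and contributes nothing to a baseline-adjusted model. An unstructured covariance over the 16 visits from 3 to 18 needs 16 × 17/2 = 136 parameters, too many for 36 subjects. The simulations used five visits, so the full model was not tested.

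**Conclusion.** The point holds as a gap in specification with a concrete remedy. The four primary tests fall back on observed cases without saying so, and this does not deliver the declared intent-to-treat analysis. The grouping by treatment received in protocol 12.1.1 is a direct textual contradiction of intent-to-treat, whatever the amount of missing data.

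The likely size is modest and its direction unknown: about -1 to +2.6 mini-RQLQ points on a 0 to 84 scale in the simulated scenarios, or up to about 0.45 of a standard error. It is near zero if the arms lose subjects alike and larger in the extreme corners of the table. These figures rest on the assumed SD, correlation and mechanisms. The 22% is an inferred maximum allowance. The more dependable gain comes from baseline adjustment, 8 to 19% off the standard error under the assumed correlations. This should be settled before database lock; it does not invalidate the trial.

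**What to change.** Amend the SAP as follows.

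1. **Population.** Analyse efficacy in all dosed subjects as randomised, and correct the treatment-received wording in protocol 12.1.1.
2. **Mini-RQLQ.** Use a mixed model on the post-baseline visits with the visit 2 score as covariate. Pre-specify a simple covariance structure or a reduced set of visits. Report the visit 17 and 18 contrasts with 95% confidence intervals. This also supplies the LS means that the protocol promises.
3. **DCS.** Use a baseline-adjusted model at weeks 10 and 14. Acknowledge that subjects lost before week 10 have no outcome, and state the imputation that covers them. Reconcile the diary weeks in 12.1.3 with Appendix A, which lists TNSS across the treatment visits.
4. **Early termination.** State which analysis visit, if any, an early-termination score feeds.
5. **Sensitivity.** Keep the observed-case t test as a sensitivity analysis, and add one that shifts imputed drop-out values for the worse.

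The cost is SAP text and modest programming, with no new data. The SAP introduction allows revisions before database lock. The price is reliance on a model and on drop-out being explained by observed scores, which item 5 probes. Only part of the precision lost to drop-out is recovered.

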#### *7.1.4 Immunotherapy Dose and Regimen*

Recruited subjects alternate to be assigned either treatment set I or II (representing either placebo or active PMA treatment in a binded fashion). The assigned treatment set will remain for the duration of the study for each subject. On the day of an injection, 0.3ml from each of the appropriate vial set mix (A-C) will be combined in a sterile 5 ml bottle. Using a new sterile syringe, 0.15-0.60ml of the PMA solution or placebo will be removed for injection purposes according to the injection schedule (Appendix I). A sterile 27G ½ inch syringe will be used for administration. Immunotherapy will be administered bi-weekly in the study clinic for a total of eight consecutive weeks. Appendix I lists the precise immunotherapy injection schedule.

All patients are required to remain in the clinic under close observation by the study nurse for a period of 30 minutes following their injection. A physician is required to be present in the clinic at all times. In addition, one of the investigators must be present on campus and available by cell phone during scheduled treatment sessions. Emergency medications such as albuterol, oxygen, diphenhydramine, and at least two epi-pens will be readily available in the treatment area.

It is important to note that the maximum concentration of each individual allergen is quite low compared to more traditional immunotherapy regimens. The maximum PNU/ml (Protein Nitrogen Units) in vial #1 will be no more than about 180 PNU/ml per allergen (eg 0.9ml of 20,000 PNU/ml stock material into 100ml solution). In most cases the actual concentration of each stock allergen is much lower than 20,000 PNU/ml since the material may be provided as a mixture of several allergens. We would estimate therefore that subjects would receive no more than about 7.2 PNU of antigen contained in the highest injection (0.2ml Vial #2). Typically, allergens are administered via immunotherapy in a range of about 2000 PNU. Thus the dosage of each allergen is less than 0.36% of a typical dose administered in our clinics. The lower overall dosing scheme provided in this study would therefore be considered to be extremely safe with minimal adverse events.

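### Efficacy is grouped by treatment received despite a stated intent-to-treat approach, and the primary t test on change leaves baseline unadjusted

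*Combined protocol and SAP*

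**What the plan says.** **Grouping rule.** Protocol 12.1.1 states: "Efficacy analyses will be analyzed according to the treatment received and safety analyses will be analyzed according to the actual treatment received". Protocol 12.1.3 states: "The intent-to-treat approach will be used", and the Efficacy Analyses part of the Study Summary says the same. The SAP has no population rule of its own. Its Study Design section says: "The SAP will follow the study protocol sections 12.1 to 12.3". Its comparisons are between groups I and II, which protocol 7.1.1 and 7.1.4 define as the vial sets to which subjects are assigned. Section 7.1.4 adds: "The assigned treatment set will remain for the duration of the study for each subject".

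**Test.** The four primary comparisons in the SAP (DCS and mini-RQLQ, visit 2 to 17 and visit 2 to 18) and the two TNSS comparisons under Secondary Outcomes each take the "change in score) between both treatment groups I and II using an unpaired t test". No covariate is named. Protocol 12.1.3 promises model-type output: "The p-value, least square (LS) treatment means, difference between the LS treatment means, and 95% confidence intervals for the treatment differences will be presented". It names neither a model nor covariates.

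**The concern.** There are two separate points.

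1. The sentence in 12.1.1 is built as a contrast between efficacy and safety, yet both halves give the same as-treated rule, and that rule conflicts with intent-to-treat. Because the SAP adopts 12.1 to 12.3 whole, it takes in both statements, while its own labels point to assignment. Two analysts could group a wrongly dosed subject differently and each cite the protocol. Moving subjects between arms according to what they received gives up the protection of randomisation for efficacy.

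2. With 28 to 36 subjects, chance differences between arms at baseline are common. A change score corrects for them with a slope fixed at 1. The visit 2 score needed to estimate that slope is already part of the planned analysis. What is at stake is precision, not bias.

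**Working it through.** **Point 1: the texts side by side**

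| Place | Rule for efficacy |
|---|---|
| Study Summary, Efficacy Analyses | intent-to-treat |
| Protocol 12.1.3 | intent-to-treat |
| Protocol 12.1.1 | treatment received (same as safety) |
| SAP Study Design | adopts 12.1 to 12.3, so both of the above |
| SAP Primary and Secondary Outcomes | groups I and II, the assigned sets |

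The rules differ in result only if someone is dosed from the wrong set. Appendix H schedules 16 injections per subject, so 36 subjects receive up to 16 × 36 = 576, each combined from three vials. The opportunity for error is not zero, but no rate is given and none is assumed here. Section 12.1.1 also does not say which treatment counts as received after a single injection from the other set. Assignment by set has no such ambiguity.

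**Point 2: precision**

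*Sample size.* The plan's 28 comes from response rates of 80% and 30%, alpha 0.05 and 80% power. The two-sided pooled formula gives [1.96 × √(2 × 0.55 × 0.45) + 0.842 × √(0.16 + 0.21)]² / 0.50² = 14.3, so 15 per arm, or 30 in total. At 14 per arm the power is 79.1%, so the stated figure is reproduced closely. It concerns a binary response, so it says nothing about the power of a t test on change. It only fixes the sizes used below: 14 per arm (28 evaluable) and 18 per arm (36 recruited).

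*Assumptions.* ρ is the baseline/follow-up correlation and k is baseline SD divided by follow-up SD. The documents give neither, so ranges are used.

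*Formula.* The variance of the ANCOVA estimate relative to the change-score estimate is (1 − ρ²) / (1 + k² − 2ρk). At k = 1 this is (1 + ρ)/2. At k = ρ it is 1: the true slope, ρ/k, is then exactly 1 and ANCOVA gains nothing.

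| | ρ = 0.3 | ρ = 0.5 | ρ = 0.6 | ρ = 0.8 |
|---|---|---|---|---|
| k = 1.0 | 0.65 | 0.75 | 0.80 | 0.90 |
| k = 0.8 | 0.91/1.16 = 0.78 | 0.75/0.84 = 0.89 | 0.64/0.68 = 0.94 | 0.36/0.36 = 1.00 |
| k = 0.6 | 0.91/1.00 = 0.91 | 0.75/0.76 = 0.99 | 0.64/0.64 = 1.00 | 0.36/0.40 = 0.90 |

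Estimating the slope adds about 1/(N − 4) to the variance: 1/24 = 4.2% at N = 28 and 1/32 = 3.1% at N = 36.

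*Power.* A simulation used 20,000 bivariate normal replicates, two-sided 0.05 and 14 per arm. The effect was set at 1.10 SD of the change score so that the t test has 80% power. ANCOVA power was:

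| | ρ = 0.3 | ρ = 0.5 | ρ = 0.6 | ρ = 0.8 |
|---|---|---|---|---|
| k = 1.0 | 92.5% | 88.8% | 86.4% | 82.4% |
| k = 0.8 | 87.4% | 82.7% | 80.6% | 77.7% |
| k = 0.6 | 82.2% | 79.2% | 78.3% | 81.8% |

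At 18 per arm and k = 1 (effect 0.96 SD) the values are 92.5%, 88.7%, 86.7% and 82.8%.

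*Interval width.* The mean ratio of ANCOVA to t test at 14 per arm runs from 0.824 (ρ = 0.3, k = 1) to 1.022 (ρ = k). As a check, √(0.65 × 1.042) = 0.82 and √1.042 = 1.02.

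*Chance imbalance.* The probability that baseline means differ by more than 0.3 SD is 2 × [1 − Φ(0.3/√(2/n))]: 0.427 at n = 14 and 0.368 at n = 18. This does not depend on ρ or k.

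**The case against.** **On the test.** A t test on change is valid in a randomised trial, and it does not strictly conflict with the promised LS means, because LS means from a treatment-only model equal the arm means. The gain from ANCOVA rests on ρ and k, which the documents do not supply, and the range includes a small loss. The 0.3 SD imbalance threshold is arbitrary. For DCS the documents point towards a low k: allergy medications are stopped in the washout, so the week 2 score is mostly TNSS among subjects selected at 6 or more. Follow-up DCS adds a rescue score expected at 0 to 6, with Appendix I steps up to 12. At k of 0.4 to 0.5 and ρ of 0.3 to 0.5, simulated ANCOVA power is 78% to 80% and intervals are 1.00 to 1.02 times as wide.

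All of this stands as a limit on the size of the benefit. It does not favour the fixed slope. In that same region a high correlation (ρ = 0.8) gives ANCOVA 86% to 91%, and baseline and follow-up scores that differ so much in content give no reason to expect a slope of exactly 1.

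**On the grouping rule.** The wording is probably a slip for treatment randomised, and adopting 12.1 to 12.3 brings in the intent-to-treat sentence too. Both are fair, but neither makes the text unambiguous. It is also true that the analysis set is a modified intent-to-treat set: "The FAS will consist of all subjects who were randomized and received at least one dose of double-blind study immunotherapy". That concerns who is included, not which arm they are counted in, so the correction is unaffected.

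**Conclusion.** Both points hold, and both should be corrected.

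The efficacy grouping rule in protocol 12.1.1 is wrong as written: it contradicts the stated intent-to-treat approach and duplicates the safety rule. Its practical effect is probably small, because each subject keeps one set and is dosed in clinic. No size is claimed.

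The unadjusted t test is valid but usually less precise than a baseline-adjusted analysis. For ρ from 0.3 to 0.8 and k from 0.6 to 1.0, moving to ANCOVA changes power at 14 per arm by about +13 to −2 points. The upper end needs similar baseline and follow-up spread and a low correlation. Entry thresholds, and for DCS the washout, make k below 1 plausible, so the gain may be small. The loss is limited to about 2 points, including in the runs at k of 0.4 to 0.5. Confidence in the size of the gain is moderate, since ρ and k are assumed.

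**What to change.** 1. In protocol 12.1.1, state that efficacy is analysed according to randomised (assigned) treatment and safety according to actual treatment. State in the SAP that groups I and II are the assigned sets.
2. In the SAP, before unblinding, make the primary analysis of each continuous outcome (DCS, mini-RQLQ, TNSS) an ANCOVA on randomised treatment and the visit 2 value. Report the LS-mean difference, its 95% confidence interval and p value. State which diary week supplies the visit 2 DCS.
3. Keep the unpaired t test on change as a sensitivity analysis.

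The cost is wording in both documents and no new data. The SAP provides for this: "Any revisions to the SAP (both alternative and additional methods) will be made prior to database lock". The statistical price is one degree of freedom, about 3% to 4% of variance.
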